2. BACKGROUND

2.1 Existing research

The NHS Health Technology Assessment (HTA) systematic review of atopic eczema treatments included a chapter on the evidence base for non-pharmacological interventions¹. This failed to identify any trials evaluating the use of water softeners for patients with atopic eczema. The only trials of possible relevance were an inconclusive trial looking at the benefits of salt baths, and another that examined the use of biological versus non-biological washing powders. This search was updated in 2006 and no new references were found

There is epidemiological evidence linking increasing water hardness with increasing atopic eczema prevalence. This was first demonstrated by the current research team in an ecological study published in *The Lancet* of 4141 randomly selected primary school children in the Nottingham area ². The 1-year period prevalence of eczema was 17.3% in the hardest water category and 12.0% in the lowest (odds ratio of 1.54, 1.19-1.99 after adjustment for confounders). Similar results have recently been found in Japan ³.

If the above associations are true, a number of plausible mechanisms can be forwarded to suggest why hard water could exacerbate eczema. Perhaps the most likely explanation is increased soap usage in hard water areas; the deposits of which can cause skin irritation in eczema sufferers. A direct chemical irritant effect from calcium and magnesium salts is also possible, or an indirect effect of enhanced allergen penetration from skin barrier disruption.

2.2 Hypothesis

- That the installation of an ion-exchange water softener will help to relieve the symptoms of eczema in children with moderate to severe eczema.
- That the installation of an ion-exchange water softener will result in cost implications to both patients and the NHS.

2.3 Benefit / risk assessment

This is very low risk trial as the intervention is non invasive with no known clinical side effects. Participants simply receive softened water for bathing and washing of clothes. Drinking water will remain unchanged.

The water softening units will be installed by a qualified water engineer according to the Code of Practice produced by British Water.

The unit to be used is a generic version of a commercially available unit which has been encased in a generic outer box in order to prevent commercial advantage for any individual water softener supplier. Ion-exchange technology is well understood and widely used throughout the world.

Possible benefits to trial participants, in addition to improvement in eczema symptoms, include reduced scaling of water appliances, reduced soap / cleaning product consumption and reduced energy consumption.

3. STUDY DESIGN

This is a single-blind, parallel group randomised controlled trial of 12-week duration, followed by a 4-week cross-over period (Figure 1). The study will be analysed as a parallel group study, but the final 4 week period will include exploratory analyses to explore within person effects. Specifically, these exploratory analyses will provide further information on (i) the speed of onset of benefit for the delayed treatment group, and (ii) on how quickly benefits are lost once treatment is removed in the active treatment group. Three hundred and ten children with moderate to severe eczema will each be enrolled into the study for a period of 16 weeks. Participants will be enrolled over a period of 18-20 months, starting in Spring 2007. The end of study is defined as being the final assessment visit of the last participant into the trial.

Figure 1: Study design

| | STUDY PERIOD = 16 weeks | | |
|---------|--|----------------|-------------------------|
| | 0 to 12 weeks | 12 to 16 weeks | |
| Group A | Usual eczema care + water softener installed (n = 155) | Unit removed | Option to purchase unit |
| Group B | Usual eczema care + delayed installation (n = 155) | Unit installed | at reduced cost |

4. OBJECTIVES

- i. To assess whether the installation of an ion-exchange water softener improves eczema in children.
- ii. If so, to establish the likely cost and cost-effectiveness of this intervention.

5. INTERVENTIONS

5.1 Treatments to be compared

Ion-exchange water softening units will be compared with usual care. Ion exchange water softening is a scientifically defined, understood and described process using a synthetic polystyrene resin in which primarily the divalent cations (positively charged), calcium and magnesium found in domestic water supplies, are replaced by the monovalent cation, sodium, from common salt. The water softener used in the study has two cylinders of resin which are used alternately. A control valve ensures that when the resin capacity of one cylinder is exhausted it automatically switches the water flow to the second cylinder and, using common salt, regenerates the first to be ready for use when the second is exhausted. Ion-exchange water softening units typically reduce the water hardness to practically zero¹.

All units will be installed in the child's principal residence and salt will be supplied for the duration of the trial. Standard procedure will be to soften all water in the home, and provide mains drinking water through an extra (faucet-style) tap installed at the side of the kitchen sink. Participants will be given the opportunity to opt out of having this

¹ By contrast, physical water conditioners affect the behaviour of calcium in water but they do not remove it. The process by which they have this effect is not fully understood scientifically and so their design is empirical. Whether or not Physical Water Conditioners have a beneficial effect on eczema is a question for future study once proof of principle has been tested using established ion-exchange technology.

separate, mains drinking water tap if they prefer.

Apart from having a unit installed in the home, participants will continue with their usual eczema treatments in the usual way and will be asked to bathe / wash their clothes according to their usual practice. The units will meet all necessary quality standards, and will be installed by a trained water engineer according to British Water's code of practice.

The water softeners to be used in this trial will be supplied and paid for by a consortium of representatives from the water treatment industry, co-ordinated through their Trade Association. The units will be encased in an unmarked box in order to prevent the possibility of commercial advantage to any particular company. Similarly, unmarked salt will be supplied for use during the trial.

Participants allocated to delayed installation will subsequently receive an active unit at week 12

During the pilot study, approval was sought from the Housing Departments of local Councils to install units in the homes of Council tenants. This was very successful and will be used again in the main trial in order to be as inclusive as possible with regards to trial participants. The relevant water companies will also be informed of the trial, and will be provided with details of the likely number of water softeners to be installed in each region.

5.2 Treatment adherence / loss to follow-up

Compliance with treatment does not represent a large problem for this trial as long as the participants are not absent from home for long periods of time. With the exception of a drinking water tap, the water is simply softened (or not) for the entire household. However, participants must remember to periodically replenish the salt (every few weeks) and it is possible that this may not be done. Evidence from the pilot study suggested that some families did use less salt than others.

In order to assess that the units are working correctly, water samples will be sent to the research team once a week. Any samples with a reading of > 20 mg/L calcium carbonate will be referred back to the engineer for investigation. Participants will also be reminded of the importance of replenishing the salt supply by telephone at 8 weeks. A weekly reminder will also be included in the child's symptom diary.

It is anticipated that loss to follow-up will be <15%. For the pilot study all of the children attended for their final appointment. Nevertheless, a previous 18-week study of treatments for children with atopic eczema run by the investigators resulted in a loss to follow-up of 15% ⁴ and we propose to adopt this as a more conservative estimate. At the end of the study all participants will be offered the chance to purchase the units at a reduced cost (£446.50 inclusive of VAT, installation and warranty; this is approximately half the full retail price).

5.3 Concomitant therapy

Participants will be allowed to use their usual eczema treatments as prescribed. However, children will be asked not to start any NEW treatments during the period of the study if medically possible. (*See also* exclusion criteria).

5.4 Rescue medication

Rescue medication will be defined by asking participants at the recruitment visit what they would do if they needed to "step-up" their treatment in response to a worsening of the eczema. The need to "step-up" treatment will then be recorded in the child's diary on a daily basis.

5.5 Starting and stopping treatment

Units will be installed in the participants' homes as soon as possible after being randomized to treatment (ideally within 10 working days).

If participants choose to withdraw from the study, any units that have been installed will be removed as soon as is practicably possible. Participants will be asked to complete an end of study questionnaire at this time and diaries will be collected.

If participants are away from the main residence for any reason, this information will be recorded in their treatment diaries. Absence from the home will be included in a predictors of response model and will be used as a measure of treatment adherence for the (secondary) per protocol analysis.

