9.4 End of Trial Follow-up Questionnaire

Parents of participants will be sent an end of trial follow-up questionnaire once all participants have completed the study. This will seek information about current eczema status, and whether or not they have a functioning water softener.

Table 1: Summary of schedule of assessment visits

| | BASELINE | Group A | "4 week" Appointment | "8 week" | "12 week" | Group A Un-installation | "16 week" |
|---|---|--|---|-------------------------------|--|---|---|
| | = Day ZERO | installation | rippointment | Reminder | Appointment | Group B Installation | Appointment |

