10.2 Sample Size estimate

Sample size estimates are based on other published data relating to the use of SASSAD in patients recruited in secondary care¹⁵, ⁵. Based on a minimum clinically relevant difference of 20% in the change in SASSAD score between the 2 groups, and assuming a mean baseline SASSAD score of 20 with a standard deviation in change scores of 10 ¹⁵, a sample size of 310 children will provide 90% power, assuming a significance level of 5% and attrition rate of 15% (see planned interventions section). Sample size estimates based on the results of the pilot study, support this sample size estimate.

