5. ITT ANALYSIS AND MULTIPLICITY

The SWET trial will be analysed as intent-to-treat (ITT) at week 12.

The ITT population will consist of all randomised participants with evaluable data. This will be the primary population used for the main analysis, which will use the randomised treatment allocation rather than actual treatment received. An additional sensitivity analysis will be performed excluding outliers.

Primary inference will be based on the primary endpoint analysis of the ITT population. Significance will be at the 5% level.

A secondary, per protocol analysis of the primary endpoint will be performed excluding the following participants:

- Those who were randomised into the study, but who failed to receive their allocated treatment.
- Those who are deemed to be major protocol violators as determined by the Protocol Violators Group (including independent members) review of the protocol deviation log.

Criteria for protocol violators are as follows:

- Missing SASSAD score at week 12
- Group A: exposed to fully softened water for <75% of the time their home has an active water softener in place (i.e. sleeping at home + unit fully working for <75% of the time their home has an installation)

- Group A: Participant away from home or with partially functioning water softener of >2 days/week for each of the 4 weeks prior to the primary outcome measure
- Group B: Participant away from home for > 2 days/week for each of the 4 weeks prior to the primary outcome measure
- Unblinding of research nurse prior to primary outcome measurement
- Starting new treatment prior to primary outcome measurement will be examined on a case-by-case basis to determine if they comprise a protocol violator.

Baseline characteristics (as described in section 6.2) will be summarised and if any major imbalance exists the analyses will be adjusted to account for this.

Analyses of all secondary endpoints and adjusted analyses will be considered supportive to the primary analysis so no adjustments for multiple comparisons will be made.

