7. PLANNED SUBGROUP ANALYSES

A sub-group analysis will be conducted based on the presence or absence of mutations on the filaggrin gene (collected using spit samples). Mutations on the filaggrin gene have been associated with dry skin and may therefore be a useful predictor of treatment success. The planned subgroup analysis will only be performed on the primary outcome of change in SASSAD score. The p-value for the interaction will be reported.

Assuming that the presence of at least one mutation in the gene encoding filaggrin results in improved treatment response, a total of 90 children with at least one such mutation would be sufficient to detect a 30% difference between the treatment groups in the primary outcome, with 80% power, 5% significance (2 sided) and a standard deviation of 10. Allowing for a 20% drop out means that 120 children would need to carry the gene mutation. For 90% power this figure would be 145.

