9.3. Withdrawals

If participants choose to withdraw from the study, any units that have been installed will be removed as soon as is practicably possible. Participants will be asked to complete an end of study questionnaire at this time and diaries collected.

The number of participants who withdraw from the study with the reasons for withdrawal will be summarised by randomised treatment allocation.

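### Families who withdraw are not asked to keep the week-12 blinded SASSAD visit, so at the planned 15% loss the primary by-allocation result would rest partly on imputed values

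*Combined protocol and SAP*

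**What the plan says.** Protocol 5.5 covers families who choose to withdraw from the study. Any unit is removed, and: "Participants will be asked to complete an end of study questionnaire at this time and diaries will be collected". SAP 9.3 gives the same rule: "Participants will be asked to complete an end of study questionnaire at this time and diaries collected". SAP 9.3 also has withdrawals and their reasons summarised by arm.

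Protocol 9.1.1 and Table 1 place nurse visits at baseline and weeks 4, 12 and 16, with no withdrawal visit. Under protocol 6.1 the SASSAD is scored by the nurse without any contribution from the participant, so a questionnaire or diary cannot replace it.

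SAP 5 compares groups by allocation, whatever treatment was received, and defines the set thus: "The ITT population will consist of all randomised participants with evaluable data". SAP 8.1 analyses complete cases if less than 5% of the primary endpoint is missing, with a sensitivity analysis that substitutes the larger of the baseline and week-4 scores. If more than 5% is missing it calls for multiple imputation, without naming the model or its variables. Protocol 5.2 expects loss below 15% and adopts 15% as the conservative planning figure; protocol 10.2 uses it in the sample size.

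**The concern.** A comparison by allocation needs the week-12 score of every randomised child. Staff who follow 5.5 and SAP 9.3 as written would collect a questionnaire and diaries from a withdrawing family and would have no instruction to keep the week-12 appointment. The child would then have no blinded score after week 4 at the latest.

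The blinded nurse score is the plan's main protection against bias from families who know their allocation (protocol 8.3), and it is the measurement these children would not give. Reasons for leaving may also differ by arm. Before week 12 only Group A has a unit, salt to replenish and weekly water samples to send; Group B is waiting for its unit. If leavers in the two arms differ in how their eczema is progressing, the comparison among children with scores is biased, and imputation corrects this only as far as its model predicts the missing scores.

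**Working it through.** **1. The plan's sample size.** Protocol 10.2 takes one fifth as the smallest difference between arms worth detecting, with these inputs: "assuming a mean baseline SASSAD score of 20 with a standard deviation in change scores of 10". So the target is 0.20 × 20 = 4 points and the SD is 10. Power is 90%, alpha 5% and attrition 15%. Two-sided testing is stated only for the subgroup calculation (SAP 7), but it is the reading that fits here: one-sided testing would give 255 in total.

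- n per arm = 2 × [10 × (1.960 + 1.282) / 4]² = 131.3, rounded up to 132, so 264 evaluable.
- 264 / (1 − 0.15) = 310.6, or 311, against 310 stated. The figure reproduces.
- With 310 × 0.85 = 263.5 evaluable, power is 90.1% (normal approximation) or 89.9% (noncentral t).

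**2. Is power at stake?** Suppose a share of the 15% still gives a week-12 score. The shares are assumptions; power is by normal approximation.

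| Share recovered | Evaluable N | Power |
|---|---|---|
| 0 | 263.5 | 90.1% |
| 50% | 286.8 | 92.3% |
| 100% | 310 | 94.1% |

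The most that could be gained is 4 percentage points above a target already met.

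**3. Which missing-data rule would apply?** 5% of 310 is 15.5 children and 15% is 46.5. Since 46.5 / 15.5 = 3, loss at the planned rate leads to multiple imputation, not to complete cases.

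**4. Possible bias under the complete-case rule.** Let w be the fraction missing in an arm and g the number of points by which leavers improve less than stayers in that arm. The true mean improvement in an arm is the stayers' mean minus w × g. The error in the complete-case difference (A minus B) is therefore w_A × g_A − w_B × g_B. The documents give no value for g. I assume 5 points, at 5% missing overall:

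| Scenario | Shift (points) | Share of 4-point target |
|---|---|---|
| 5% in each arm, same gap | 0.05×5 − 0.05×5 = 0 | 0 |
| 3.33% in A, 6.67% in B, same gap | 0.0333×5 − 0.0667×5 = −0.17 | 4% |
| 5% in each arm, gap in one arm only | 0.05×5 = 0.25 in size | 6% |

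For the last row, a gap of 2 to 10 points gives 0.1 to 0.5 point. The 0.25 is not a bound even at a 5-point gap: if all 15.5 losses fell in one arm of 155 (10%), the shift would be 0.10 × 5 = 0.5 point.

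**5. Above 5%.** The bias left after imputation cannot be computed from the documents, because the imputation model is not given.

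**The case against.** The exit rule applies only to families who choose to leave the study. A reader might infer that giving up the unit also ends assessment. The documents do not say that. SAP 5 keeps children with too little exposure, a faulty unit or no allocated treatment in the intention-to-treat set and removes them only from the per-protocol set, where a missing week-12 SASSAD is a separate criterion. This part of the objection stands.

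A reader might also compute complete-case shifts at 15% loss, for example 0.15 × 5 = 0.75 point, or 0.10 × 5 − 0.20 × 5 = −0.5 point. SAP 8.1 would not run a complete-case primary analysis at that loss, so these figures do not describe the planned result.

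Nor can the exit questionnaire be judged from protocol 9.4. The form described there ("This will seek information about current eczema status, and whether or not they have a functioning water softener") goes out once all participants have finished, and SAP 11 says the end-of-trial questionnaire was added part way through. The content of the form completed at withdrawal is not described.

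The point rests on silence: nothing forbids a week-12 score after withdrawal. The information and consent documents were not available here, so what families were told cannot be checked. Some families will refuse. Loss may also be lower than planned: all pilot children attended their final appointment (protocol 5.2), and Group B has a reason to stay until its unit arrives. SAP 8.1 and 9.3 also report missing outcomes and withdrawals by arm, with reasons where available.

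These points limit the size of the concern but do not fill the gap. Two sections set out what is collected at withdrawal, and neither includes the primary outcome or an invitation to the visit that provides it. Reporting and imputing missing scores does not replace measuring them.

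**Conclusion.** The point holds for families who withdraw from the study. As written, the plan gives up week-12 primary scores that some of them would probably provide. That any are obtainable is an inference: these families are already to be contacted about the questionnaire and diaries, and protocol 8.4 allows the recruitment appointment to take place at home.

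At the planned 15% loss, the primary result would depend partly on an unspecified imputation model. In the complete-case range an assumed 5-point gap gives shifts from 0 to about 0.25 point when loss is equal between arms, and more if loss is concentrated in one arm. Neither the gap nor the split of losses comes from the documents, so these figures illustrate scale and do not estimate bias. A reader might infer a power shortfall; the reproduced sample size rules that out.

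**What to change.** In protocol 5.5 and SAP 9.3, state that a child who withdraws is still invited to the scheduled week-12 blinded SASSAD and POEM unless the family refuses further contact, and that these scores are analysed in the arm as randomised. The trial manager, who already knows allocation, can make the invitation so that the nurse does not learn the reason.

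If the family declines week 12, a single SASSAD at exit may be requested. It is not the primary endpoint and should serve only as an auxiliary variable in the imputation model. It should be arranged separately from any unit removal, because before week 12 only Group A has units and a joint visit could reveal allocation.

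The cost is wording in two sections, matching participant information and some extra scheduling; nurses, visit and scale are already in place. There is a small risk to nurse blinding, which protocol 13.2 protects by keeping nurse contact to a minimum after recruitment. Only part of the loss will be recovered. Group A scores taken after a unit has gone will include time off softened water, which is part of what a by-allocation comparison measures.

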6. OUTCOME MEASURES

6.1 Primary outcomes

1. Difference between the active vs. standard treatment groups with regard to mean change in disease severity (Six Area Six Sign Atopic Dermatitis Score – SASSAD ⁵) at 12 weeks compared to baseline. SASSAD is an objective severity scale that is completed by the research nurse during follow-up appointments. It does not involve input from the participant in any way.

6.2 Secondary outcomes

1. Difference between the groups in the proportion of time spent moving during the night². Movement will be captured for periods of one week at week 1 and week 12, and will be measured using accelerometers (ActiwatchTM). These units are worn by the child in the same way as a wrist watch

² This outcome has been included as an objective surrogate for sleep loss and itchiness (two of the defining features of eczema). Previous research has suggested that this is a suitable objective tool for assessing itch ^{6,7} and further pilot work is currently underway to assess its suitability for use within this trial (results available Dec 2006)

This outcome has been included as an objective surrogate for sleep loss and itchiness (two of the defining features of eczema). Previous research has suggested that this is a suitable objective tool for assessing itch ^{6,7} and further pilot work is currently underway to assess its suitability for use within this trial (results available in 2007).

- 2. Difference in proportion of children who report either good or excellent improvement in eczema severity at 12 weeks (using a 5-point Likert scale).
- 3. Difference in the amount of topical corticosteroid / calcineurin inhibitors used during the 12 week study period.
- 4. Difference in Patient Oriented Eczema Measure (POEM ⁸) collected at baseline, weeks 4, 12 and 16. This scale is a well validated tool that has been developed to capture symptoms of importance to patients (rather than objective signs that are used in traditional severity scales, such as SASSAD).
- 5. Difference in the number of totally controlled weeks (TCW) and well controlled weeks (WCW) based on the number of days with eczema symptoms and the number of days that topical treatment is applied. This outcome is based on a recent systematic review conducted by the applicants looking at ways of assessing long-term control for chronic conditions such as atopic eczema, asthma and rheumatoid arthritis ⁹. The terms TCW and WCW have been adopted for use by researchers in the field of asthma and appear to be a useful and intuitive means of capturing disease activity over time.
- 6. Difference in the mean change in the Dermatitis Family Impact (DFI) questionnaire at 12 weeks ¹⁰. This scale was chosen as an appropriate quality of life scale for the study for two reasons:
 - The intervention involves the entire household, so a quality of life scale appropriate to the family unit seems most appropriate.
 - It avoids the need to use two different age-specific dermatology quality of life scales (the Children's Dermatology Life Quality Index¹¹ and the Infants version of the same scale¹²).
- 7. Mean change in health related Quality of Life at 12 weeks. This will be captured using a generic measure of health utility (the children's version of the EQ-5D for children aged 7 years and over, or the proxy version of the EQ-5D for children aged 3 to 6 years ¹³).

